3.2 Subject Selection

3.2.1 Recruitment and Informed Consent

Various methods of recruitment may be used such as advertising, referrals, or solicitation of subjects previously known to the clinical site. Interested subjects will be invited to participate in the informed consent process. Informed consent will be obtained by the use of a written consent

form approved by the Institutional Review Board (IRB) or Independent Ethics Committee (IEC) and signed and dated by the subjects at the time of consent. Subjects will be interviewed to ensure that the subjects meet all entry criteria relating to history. The clinical investigator or designee will conduct the consent discussion on an individual basis with each subject and will allow adequate time for all questions to be addressed. Written informed consent will be obtained prior to conducting any study-related procedures. A copy of the signed consent form shall be given to the subjects on the day of study entry.

3.2.2 Screening

After informed consent is obtained, a unique screening number will be assigned to each subject for identification purposes, and the subject will be screened to assess eligibility for the study. A screening log will be maintained by the site that records all subjects for whom consent was obtained and who entered the screening process. Screening log will record name, birth date, sex, ethnicity and race. Abnormal results and findings resulting in ineligibility will be discussed with the subject who will be referred for follow-up care with their healthcare provider if necessary.

Eligibility for entry into the study will be based on the inclusion and exclusion criteria described below. Results of the urine pregnancy test must be known before enrollment. The investigator must document confirmation of eligibility prior to randomization

3.2.3 LRG Inclusion Criteria

Subjects must meet all of the following criteria at the time of subject ID assignment:

1. History of dog, cat, mongoose, fox, ferret, skunk, bat or raccoon bite to trunk, leg, ankle or foot, or lick or scratch with, or of broken skin or mucous membrane saliva or neural tissue contamination, unprotected physical bat contact, scratch or saliva contamination of the head or neck without broken skin all \leq 54 hours (Section 3.9.4 and 3.9.5)
2. Has completed the written informed consent process and signed informed consent document
3. Males and females
4. Is age \geq 18 years on Study Day 1
5. Agrees to stay in contact with the study site for the duration of the study, provide updated contact information as necessary, and has no current plans to move from the study area for the duration of the study
6. Lives within 2 hour journey by available transportation to study center
7. For female subjects: agrees to avoid pregnancy from Study Day 1 through Study Day 121. Women physically capable of pregnancy (not sterilized and still menstruating or within 1 year of the last menses if menopausal) in sexual relationships with men must use an acceptable method of avoiding pregnancy during this period. Acceptable methods of avoiding pregnancy include a sterile sexual partner, sexual abstinence (not engaging in sexual intercourse), hormonal contraceptives (oral, injection, transdermal patch, or implant), vaginal ring, intrauterine device (IUD), or the combination of a condom or diaphragm with spermicide

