2.2.1 Low Risk Group (LRG)

The Low Risk Group (LRG) is composed of subjects who meet the modified WHO Category 3 protocol exposure criteria (Table 2.2-1 below and Sections 3.9.4 and 3.9.5). Inclusion is limited to bites to the foot, ankle, leg or trunk and licks to broken skin, scratches with, or to broken skin, unprotected bat exposure or mucous membrane contamination by saliva or neural tissue. These exposures represent a lower rabies risk exposure within WHO Categories 3. Bites to the head, neck or genitalia are excluded from LRG Initial Enrollment and LRG General Enrollment (Section 2.2.2 to Section 2.2.4). The purpose of the LRG is to obtain early safety, pharmacodynamic and pharmacokinetic information from field sites. Since it does not have the same rabies risk as the NRG it, will be analyzed separately for clinical rabies.

Table 2.2-1 Exposure Characteristics of the Low Risk Group and Normal Risk Group

Exposure Type	LRG	NRG
Head and neck bite	-	+
Genitalia bite	-	+
Arms bite	-	+
Hands bite	-	+
Trunk bite	+	+
Legs bite	+	+
Ankles bite	+	+
Foot bite	+	+
Non-bite lick	+	+
Non-bite scratch	+	+
Non-bite bat contact	+	+
Non-bite mucous membrane	+	+

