3.2.6 Major Protocol Deviations and Eligibility for the Per-protocol Population

Continuation in the per-protocol population depends on the absence of uncorrectable major protocol deviations. Major deviations are those that would degrade the fidelity of the data from the protocol. Protocol deviations requiring removal from the per-protocol population include but are not limited to those listed below.

- Defective informed consent
- Received the incorrect Study Drug
- Received the incorrect dose ($\pm 20\%$) of Study Drug
- Failed to complete the scheduled rabies vaccinations through Study Day 29
- Are discovered to lack adequate prophylactic treatment of all exposure sites
- Are discovered to be injured by animal other than those listed
- Are discovered to have an interval > 54 hours from rabies exposure to the start of prophylaxis
- Are discovered to have RVNA ≥ 0.1 IU in serum obtained at Study Day 1
- Receives prohibited treatment during the trial
- Are found not to have a modified WHO Category 3 exposure (Table 2.2-1, Section 3.9.4)
- Are discovered to have or have developed HIV infection or other immunodeficiency state.
- Second high risk animal bite or contact requiring PEP

Subjects who are discovered to not have satisfied any criteria for the per-protocol population may be excluded from that population (Section 3.2.8). These deviations may become known at different intervals from randomization. Likely intervals for discovery of these deviations are listed in Table 3.2.6-1 based on the occurrence of site review, monitoring visits and vaccination schedules.

Table 3.2.6-1 Intervals for Per-protocol Exclusions (approximate)

Major Protocol Deviation	Rationale	Likely Interval Days
Defective consent	Data without effective consent cannot be used	43
Diagnosis of HIV after enrollment	New HIV may affect PEP response	365
Received incorrect study drug	Mixes SYN023 and HIRG results	43
Incorrect dose ($\pm 20\%$) of Study Drug	Arbitrary but reasonable dose margin. Used for biosimilars.	43
> 54 hr from rabies exposure to the Study Drug	Early PEP initiation is important Should be discovered early from wound state and investigation	15
Failed to complete all rabies vaccinations	Important feature of PEP. Should be known by Study Day 29	29

Failure to treat all exposure sites	Documented cause of treatment failure. Should be discovered early from wound state and investigation	15

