3.9.4 Modified WHO Rabies Risk Exposure Categories

In countries or areas enzootic for rabies, exposure to suspected or confirmed rabid (domestic or wild) animals is categorized as follows (WHO 2013):

Category I: touching or feeding animals, licks on intact skin, contact of intact skin with secretions or excretions of a rabid animal or human. These are not regarded as exposures, and no PEP is required.

Category II: nibbling of uncovered skin, minor scratches or abrasions without bleeding. Vaccine should be administered as soon as possible.

Category III: single or multiple transdermal bites OR scratches to broken skin OR licks

on broken skin OR contamination of mucous membrane with saliva or neural tissue from licks or exposure to bats. Vaccine and rabies immune globulin should be administered as soon as possible.

For this protocol “exposure to bats” means a subject with unprotected (e.g. without gloves or other similar barriers) physical contact with a bat. Mucous membrane contamination means the transfer of saliva or neural tissue from the suspect animal into the eyes, nose or mouth of the victim.

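### LRG inclusion criterion 1 lists head or neck contact without broken skin as a qualifying exposure, which conflicts with the protocol's own Category 3 definition and with the per-protocol rule built on it.

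*Protocol*

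**What the plan says.** Protocol Section 3.2.3, criterion 1, lists the exposures that qualify a subject for the LRG: certain bites, licks or scratches involving broken skin, mucous membrane contamination and unprotected bat contact. It then adds "scratch or saliva contamination of the head or neck without broken skin" and refers the reader to Sections 3.9.4 and 3.9.5.

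Section 3.9.4 sets out the categories:
- Category I is "touching or feeding animals, licks on intact skin, contact of intact skin with secretions or excretions of a rabid animal or human", of which the section says "These are not regarded as exposures, and no PEP is required".
- Category II is "nibbling of uncovered skin, minor scratches or abrasions without bleeding". Vaccine is named for it; immune globulin is not.
- Category III begins "single or multiple transdermal bites OR scratches to broken skin OR licks". The licks must also be on broken skin, and the remaining routes are mucous membranes and bats. Both vaccine and immune globulin are named.

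Section 2.2.1 defines the LRG: "Inclusion is limited to bites to the foot, ankle, leg or trunk and licks to broken skin, scratches with, or to broken skin", followed by bat and mucous membrane exposures. SAP Section 3.1.1 repeats this. Section 3.2.6 lists "Are found not to have a modified WHO Category 3 exposure" among the deviations that call for removal from the per-protocol population, and SAP Section 5.2 carries the same item.

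**The concern.** The entry rule and the analysis-set rule do not admit the same people. A site that reads criterion 1 as written can randomize a subject whose only exposure is saliva on intact skin of the neck, or a scratch of the face that did not break the skin. That subject has complied with the protocol at entry, yet lacks the exposure on which the per-protocol set depends.

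Two things are at stake. The first is exposure to study drug: such a person could receive SYN023 or HRIG although Section 3.9.4 names immune globulin only for Category III. The second is the LRG data: the subject may leave the LRG per-protocol set without replacement while remaining in the as-treated set, and the DSMB uses LRG data to decide whether the trial advances.

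**Working it through.** No sample size, power or rate is involved, so the check is a comparison of texts.

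**Step 1: what the clause covers under Section 3.9.4.**

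| Exposure admitted by the clause | Place in 3.9.4 | Category 3? |
|---|---|---|
| Saliva on head or neck, skin intact | Category I | No |
| Minor scratch of head or neck, no bleeding | Category II | No |
| Saliva in eyes, nose or mouth | Category III, but criterion 1 lists it separately as mucous membrane contamination | Yes, without the clause |
| Bat contact | Category III, but criterion 1 lists it separately | Yes, without the clause |

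The only exposures that the clause adds are ones that 3.9.4 does not place in Category III.

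**Step 2: whether other sections support the clause.**
- Section 2.2.1 and SAP 3.1.1 limit non-bite LRG entry to broken skin, bat or mucous membrane exposure.
- Section 3.9.3 says that all subjects should have a Category 3 exposure, and points to 3.9.4.
- Section 3.9.5 describes a scratch exposure as one to broken skin or one that breaks it.
- The protocol-specific definitions in 3.9.4 cover bat exposure and mucous membrane contamination. Neither adds intact head or neck skin.
- NRG criterion 1 (Section 3.2.4) has no such clause, although Table 2.2-1 shows every LRG exposure type as also eligible for the NRG.

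**Step 3: whether a later screen catches the subject.** None of the 13 exclusion criteria in Section 3.2.5 bars a non-Category 3 exposure. Exclusion 2 concerns only Category 3 exposures older than 54 hours. Section 3.2.8 gives the Per-protocol Adjudication Board its role because some criteria cannot be known at randomization. Here the fact that would disqualify the subject is the fact that admitted the subject, and it is known on Study Day 1.

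**Step 4: what happens in analysis.** Section 3.2.6 makes lack of a modified Category 3 exposure a deviation calling for removal. SAP 5.2 says that subjects with it are excluded, and SAP 4.3.4 requires Category 3 to be confirmed. Sections 3.2.6 and 3.2.8 and SAP 4.3.4 also say that such subjects may be excluded, with the board deciding. Section 2.7 rules out replacement. Under SAP 4.3.3 the subject stays in the as-treated population.

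**Step 5: how many subjects are open to this.** The LRG has 20 + 60 = 80 subjects, with 15 + 30 = 45 on SYN023 and 5 + 30 = 35 on HRIG. General enrollment has 30 per arm, so one removal there is 1/30 = 3.3% of that arm's general enrollment. This is a unit of scale only, since the documents do not say how often the exposure would occur.

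**The case against.** The best case for leaving the text alone is that criterion 1 should not be read in isolation. It cites 3.9.4 and 3.9.5, Section 2.2.1 limits LRG entry, and Section 3.9.3 asks for Category 3 in all subjects, so a careful site would not enrol such a person. The sentence is also poorly punctuated. The clause directly follows bat contact and could be read as describing it. Table 2.2-1 marks non-bite scratch as eligible with no mention of broken skin. Part of this stands: the conflict may come from drafting rather than intent. But the bat reading is the less natural one, because bat contact is already an item in the list, and ambiguity in an eligibility criterion is itself a reason to repair it.

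A reader might also infer more than the documents support:
- **That removal is certain.** Mandatory and permissive wording coexist, and the board weighs the impact of the deviation. Removal is prescribed but not automatic.
- **That each case costs 1 of 15 or 1 of 5 in the initial cohort and so disturbs the first DSMB decision.** SAP Section 1 and Table 4.1-1 place that cohort under protocol version 2.0, whose criterion is not shown. The protocol's change table compares version 6.0 only with version 4.0. The RVNA condition at that first decision (Section 5.1.5.2) also concerns SYN023 recipients only.
- **That the primary result is affected.** SAP Section 8.1 runs the primary efficacy analyses on the NRG per-protocol population.
- **That assignment of broken-skin scratches of the head or neck is left open.** This is largely settled: Section 2.2.1 and Table 2.2-1 bar only certain bites from the LRG and put no body-site limit on scratches.

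**Conclusion.** The contradiction is real. On its plain reading, the extra clause in LRG criterion 1 admits exposures that Section 3.9.4 does not class as Category III, and no exclusion criterion stops them. A subject entered this way could receive study drug without a Category 3 exposure as the protocol defines it, and would then meet a listed per-protocol deviation.

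The reach is limited to the LRG per-protocol set, the LRG data that the DSMB reviews and LRG subjects' exposure to study drug. At most 80 subjects are in range, and for the 20 initial subjects the documents do not show that the clause applied. The number actually affected cannot be estimated from the documents. No primary inference changes. The conclusion assumes that the clause is a separate item in the list, covering all the listed animals. If it was meant only to describe bat contact, the fault is one of wording, but the sentence still needs repair.

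**What to change.** Reconcile Protocol Section 3.2.3, criterion 1, with Sections 2.2.1, 3.2.6, 3.9.3, 3.9.4 and 3.9.5 and with SAP Sections 3.1.1, 4.3.4 and 5.2, so that the LRG entry criterion and the Category 3 per-protocol rule admit the same exposures. It would be tempting to ask simply that the clause be struck, but that would choose between two eligibility rules that determine who receives immune globulin. The choice belongs to the sponsor, and this point does not make it.

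No separate SAP rule is needed for subjects already enrolled through the clause. SAP 4.3.3, 4.3.4 and 5.2 already keep them in the as-treated set and bring them to per-protocol adjudication.

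The cost is a short protocol amendment, with matching SAP wording if the Category 3 rule is the one that changes. If the entry criterion is the one that changes, LRG intake would be narrower by an amount that the documents do not allow one to estimate.

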3.2.4 NRG Inclusion Criteria

Subjects must meet all of the following criteria at the time of subject ID assignment:

1. History of dog, cat, mongoose, fox, ferret, skunk, bat or raccoon bite to any body part, lick or scratch with, or of broken skin, mucous membrane saliva or neural tissue contamination, or unprotected physical bat contact all \leq 54 hours from PEP (Section 3.9.4 and 3.9.5)
2. Has completed the written informed consent process and signed informed consent document.
3. Males and females
4. Is age \geq 18 years on Study Day 1
5. Agrees to stay in contact with the study site for the duration of the study, provide updated contact information as necessary, and has no current plans to move from the study area for the duration of the study
6. Lives within 2 hour journey by available transportation to study center
7. For female subjects: agrees to avoid pregnancy from Study Day 1 through Study Day 121. Women physically capable of pregnancy (not sterilized and still menstruating or within 1 year of the last menses if menopausal) in sexual relationships with men must use an acceptable method of avoiding pregnancy during this period.
Acceptable methods of avoiding pregnancy include a sterile sexual partner, sexual abstinence (not engaging in sexual intercourse), hormonal contraceptives (oral, injection, transdermal patch, or implant), vaginal ring, intrauterine device (IUD), or the combination of a condom or diaphragm with spermicide

3.2.5 Exclusion Criteria LRG and NRG

Subjects must have had none of the following at the time of subject ID assignment:

1. Clinical evidence of rabies infection
2. Category 3 exposure $>$ 54 hours before Study Drug receipt
3. History or serological evidence of previous rabies vaccination
4. Previous receipt of equine or human rabies globulin
5. History of hypersensitivity reaction to equine or human immunoglobulin.
6. Received immunoglobulin or blood products within 42 days before Study Day 1
7. Received any investigational drug therapy or investigational vaccine within 60 days before Study Day 1
8. Planned participation in any other investigational study during the study period.
9. Receiving systemic immunosuppressant medication such as systemic corticosteroids but not limited to systemic corticosteroids
10. History or laboratory evidence of any past, present, or possible immunodeficiency state including but not limited to any laboratory indication of HIV infection
11. Previous medical history that may compromise the safety of the subject in the study according to the opinion of the principal investigator
12. History or evidence on physical examination of any systemic disease or any acute or chronic illness that, in the opinion of the investigator, may interfere with the evaluation of the safety or activity of SYN023
13. Pregnancy (results of the urine pregnancy test MUST be known before enrollment)

3.2.6 Major Protocol Deviations and Eligibility for the Per-protocol Population

Continuation in the per-protocol population depends on the absence of uncorrectable major protocol deviations. Major deviations are those that would degrade the fidelity of the data from the protocol. Protocol deviations requiring removal from the per-protocol population include but are not limited to those listed below.

- Defective informed consent
- Received the incorrect Study Drug
- Received the incorrect dose ($\pm 20\%$) of Study Drug
- Failed to complete the scheduled rabies vaccinations through Study Day 29
- Are discovered to lack adequate prophylactic treatment of all exposure sites
- Are discovered to be injured by animal other than those listed
- Are discovered to have an interval > 54 hours from rabies exposure to the start of prophylaxis
- Are discovered to have RVNA ≥ 0.1 IU in serum obtained at Study Day 1
- Receives prohibited treatment during the trial
- Are found not to have a modified WHO Category 3 exposure (Table 2.2-1, Section 3.9.4)
- Are discovered to have or have developed HIV infection or other immunodeficiency state.
- Second high risk animal bite or contact requiring PEP

Subjects who are discovered to not have satisfied any criteria for the per-protocol population may be excluded from that population (Section 3.2.8). These deviations may become known at different intervals from randomization. Likely intervals for discovery of these deviations are listed in Table 3.2.6-1 based on the occurrence of site review, monitoring visits and vaccination schedules.

Table 3.2.6-1 Intervals for Per-protocol Exclusions (approximate)

Major Protocol Deviation	Rationale	Likely Interval Days
Defective consent	Data without effective consent cannot be used	43
Diagnosis of HIV after enrollment	New HIV may affect PEP response	365
Received incorrect study drug	Mixes SYN023 and HIRG results	43
Incorrect dose ($\pm 20\%$) of Study Drug	Arbitrary but reasonable dose margin. Used for biosimilars.	43
> 54 hr from rabies exposure to the Study Drug	Early PEP initiation is important Should be discovered early from wound state and investigation	15
Failed to complete all rabies vaccinations	Important feature of PEP. Should be known by Study Day 29	29

Failure to treat all exposure sites	Documented cause of treatment failure. Should be discovered early from wound state and investigation	15
Exposure from animal not in inclusion criteria	Some not animals don't transmit rabies. Should be discovered early from wound state and investigation	15
Serum RVNA \geq 0.1 IU at Study Day 1	Indicates previous Rabies vaccination. Results from central reference laboratory needs shipment, processing and return of results	43
Receives prohibited treatment during the trial	Has potential to increase or decrease vaccine protection. Will turn up in monitoring visit	365
Are found not to have a modified WHO Category 3 exposure (Table 2.2-1, Section 3.9.4)	Different rabies risks. Should turn up in local investigation or monitoring	15
Second high risk animal bite or contact requiring PEP	Subjects should have same rabies risk. Should turn up in monitoring.	365

3.2.6.1 Pregnancy During Study

Results of the urine pregnancy test MUST be known before enrollment. Subjects who have a positive pregnancy test on Study Day 1 should not be enrolled since this is an exclusion criteria. If a subject becomes pregnant during the study, she will continue in the study. She will not be withdrawn from the per-protocol population by the Per Protocol Adjudication Board unless she declines phlebotomy. If she wishes to withdraw study consent she should be asked to complete follow-up visits without phlebotomy. Follow-up should continue for pregnancy outcome including premature terminations, and data are to be included in the safety reports.

3.2.7 Screening Clinical Assessments and Laboratory Tests

Subjects will provide a detailed medical history and will undergo a physical examination. Demographic characteristics (date of birth, gender, and race/ethnicity) will also be collected. Any new abnormal findings will be discussed with the subject and referral will be made for follow-up care if necessary. Subjects who are discovered to have newly diagnosed HIV will undergo formal counseling and referral.

All screening laboratory specimens will be processed according to laboratory SOPs available from the clinical laboratory(ies) designated for the study. Information about the laboratory(ies), including any instructions for performing and interpreting specific tests, will be maintained in the investigator's study files.

Screening laboratory tests will be collected on Study Day 1. Results from these laboratory tests will serve as study-entry baseline values. Findings that might later make the subject ineligible such HIV status will be discussed with the subject and the subject will be referred for follow-up care with their healthcare provider if necessary. Urine Pregnancy test results MUST be known before randomization.

The study has inclusion and exclusion criteria that are required for entry on the study. Those that are knowable on Study Day 1 prior to study entry will determine eligibility for randomization. Since the results of all of the screening assessments may not be known at the time of randomization subjects may be found to be ineligible for the per protocol population after randomization. For example an individual may be found to have serological evidence of previous rabies immunization when the RVNA results are returned. This subject may continue on the trial but will be excluded from the per protocol population.

